Going Protocol title

**Pilot randomized control trial of smartphone-enabled breath alcohol monitoring on perceived fitness to drive a vehicle among intoxicated adults**

Short Title BrAC monitoring and Perceived Fitness to Drive Among Intoxicated Adults

Brief description of the protocol Please provide, in 500 characters or less, a description of the purpose of the study, the targeted population and the procedures/interactions/interventions necessary for participation.

The **goal of this study** is to conduct a laboratory-based pilot randomized control trial of smartphone-enabled breath alcohol monitoring on perceived fitness to drive a vehicle among intoxicated adults. We will enroll up to 30 adults aged  $\geq 21$ -44 who are frequent drinkers without dependence who drive more than four times per week to complete a standardized alcohol drinking protocol in a monitored setting collecting breathalyzer measurements. The protocol involves consuming three weight-based doses of alcohol with a target BAC of 0.10 and completing breathalyzer measurements every 20 minutes until a BAC of 0.03 is reached. The control group would complete a visual analog scale on their perceived fitness to drive and be blinded to their breath alcohol readings with the BACtrack Mobile Pro device, while the intervention group would do the same, but be shown their breath alcohol readings on the paired BACtrack smartphone application. Our previous research has validated the accuracy of the BACtrack Mobile Pro device to measure BAC within  $+$ / $- 0.001$  of police-grade breathalyzer and estimate BAC within  $+$ / $- 0.01$  of a blood test.

Submission type

Social and Behavioral Sciences

Is this a response to an already submitted Initial Review? NO

Human Source Material\*Does this research include collection or use of human source material (i.e., human blood, blood products, tissues or body fluids)? No

Does the research proposal involve the use and disclosure of research subject's medical information for research purposes? NO

CTRC Resources: Does the research involve CTRC resources? YES

Pathology and Laboratory Medicine Resources\*

Will samples be collected by hospital phlebotomy and/or processed or analyzed by any of the clinical laboratories of the University of Pennsylvania Health System? NO

Does this research involve collection of blood products in the Penn Donor Center and/or the use of apheresis for treatment or collection of cells or other blood components? NO

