Arm 1 (Control): Participants randomized to this arm will consume three weight-based doses of alcohol with a target BAC of 0.10 and complete breathalyzer measurements every 20 minutes until a BAC of 0.03 is reached. They will complete a visual analog scale (the Self-Reported intoxication Survey) on their perceived fitness to drive and be blinded to their breath alcohol readings with the BACtrack Mobile Pro device.

Arm 2 (Intervention): Participants randomized to this arm will consume three weight-based doses of alcohol with a target BAC of 0.10 and complete breathalyzer measurements every 20 minutes until a BAC of 0.03 is reached. They will be shown their breath alcohol readings with the BACtrack Mobile Pro device before completing a visual analog scale (the Self-Reported intoxication Survey) on their perceived fitness to drive.

Because of the limited availability of the Bactrack Skyn measurement tool in our previous trial (please reference IRB #825273, “Reducing Risky Drinking using Smartphone Paired Breathalyzer”), we will continue to test the validity of this device with the BacTrack Mobile Pro breathalyzer throughout this protocol.

Method for Assigning Subjects to Groups: Describe how subjects will be randomized to groups.

All participants who meet eligibility criteria and provide written consent will then be randomized at the time of study enrollment using block randomization.

Administration of Surveys and/or Process\*: Describe the approximate time and frequency for administering surveys For surveys, questionnaires and evaluations presented to groups and in settings such as high schools, focus group sessions or community treatment centers explain how the process will be administered and who will oversee the process. For instance, discuss the potential issues of having teachers and other school personnel administer instruments to minors who are students especially if the content is sensitive in nature. Describe the procedure for audio and videotaping individual interviews and/or focus groups and the storage of the tapes. For instance, if audio tape recording is to be used in a classroom setting, describe how this will be managed if individuals in the class are not participating in

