Some participants will wear the BACtrack Skyn wrist device, which will start collecting alcohol measurements after the first dose of alcohol. Participants will then receive three doses of vodka mixed with juice based on their gender and weight designed to reach a peak blood alcohol level of .10 g/dL. After each dose, their Breath Alcohol Content (BrAC) will be measured using the BacTrack Mobile device. After each breathalyzer measurement, participants will receive the Self-Report of Intoxication Survey, which will include Perceived Driver Fitness and Perceived intoxication and BAC estimation, which are measured using a visual analogue scale.

For the control group, participants will remain blinded to the BrAC readings on the BacTrack mobile app. For the intervention group, the participants will be shown their BrAC readings on the BacTrack mobile app before completing their Self-Report of Intoxication Survey.

Besides a preliminary study visit for participants to consent to the study and complete the eligibility survey, all research activities will take place in one of the four CTRC study sites and will occur in a study session of approximately six hours in length with up to four participants at each session. Participants will be separated into different research rooms at the CTRC.

Data collection will include contact information, medical history, and history of alcohol use, various measurements of Breath Alcohol Content (BrAC), as well as survey data from the self-reported

intoxication survey. The informed consent process during study enrollment will describe all of these aspects of data collection.

Attached to this protocol are the following study instruments for data collection and recruitment:

1. Written Informed Consent
2. Screening Survey
3. Eligibility Survey
4. Intake Survey
5. Decision making survey
6. Self-Reported intoxication Survey

Describe how and who manages confidential data, including how and where it will be stored and analyzed. For instance, describe if paper or electronic report forms will be used, how corrections to the report form will be made, how data will be entered into any database, and the person(s) responsible for creating and maintaining the research database. Describe the use of pseudonyms, code numbers and how listing of such identifiers will be kept separate from the research data.

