In a controlled setting, up to 30 participants, aged 21-39, will attend a session where they receive 3 doses of a standard amount of alcohol, based on weight and gender(Watson, Watson, & Batt, 1981), designed to raise Blood Alcohol Content to 1.02g/dL. Participants will receive their first dose of alcohol. After 30 minutes, breath alcohol content (BrAC) will be measured with the BacTrack Pro (BACtrack Mobile Pro, n.d.). To continue assessing the validity of the BacTrack Skyn device, some participants will be instructed to wear the Bactrack skyn at the beginning of the study.

For participants in the control group, they will remain blinded to their BrAC reading and complete the Self-Report of Intoxication Survey. For participants in the intervention group, they will be shown their BrAC reading on the BacTrack mobile app and then instructed to complete the Self-Report of Intoxication Survey.

A second dose and third dose will be given and this process will be repeated at 40 minutes and 80 minutes after the first dose. A study smartphone will be used to collect smartphone-paired breathalyzer readings. We will also measure self-reported intoxication rating using measures subjective intoxication: Personal Drinking Habits Questionnaire (PDHQ)(Vogel-Sprott, 1992), Perceived Driver Fitness(Van Dyke & Fillmore, 2014)and Perceived intoxication and BAC estimation(Harrison & Fillmore, 2005; Harrison, Marczinski, & Fillmore, 2007) administered by the study staff.

All research activities will be conducted in the CTRC and alcohol will be provided from Investigational Drug Service. All research staff will be fully trained in the pilot protocol and their role in the study, will be supervised by the PI, [name] [name], MD (Assistant Professor of Emergency Medicine), and will be trained to refer patients to the appropriate provider (emergency department, outpatient doctor/clinic, social worker) as warranted. A nurse, trained in the protocol, will be onsite at all times and able to assist if any adverse effects occur.

Study duration. List projected overall duration of the study including: 1. Estimated length of time to enroll all subjects and complete the study; 2. Length of a subject's participation time in study; 3. Project date of the proposed study.

Recruitment will take place for one month before the first study date, in order to enroll up to 30 participants in the study. Each subject will participate in one 5-6 hour study session. There will one to

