#### Timeline: Study activities at Site Visit

Time	Procedures *
00 - 10 minutes	
 
Participant is given a priming dose of alcohol containing vodka in fruit juice designed to raise the BrAC to 0.03-0.04 g/dL based on calculations based on weight and gender
 

10-30 minutes	
 
Participant rinses with alcohol free mouthwash or water
 

30-40 minutes	
 
Measurement of BrAC with BacTrack mobile breathalyzer
 
Control: Blinded to BrAC reading. Intervention: Shown BrAC reading on BacTrack mobile app
 
Self Report of Intoxication Survey
 

40-50 minutes	
 
Second dose of alcohol designed to raise BrAC to 0.07-0.08'
 

50-70 minutes	
 
Participant rinses with alcohol free mouthwash or water
 

70-80 minutes	
 
Measurement of BrAC with BacTrack mobile breathalyzer
 
Control: Blinded to BrAC reading. Intervention: Shown BrAC reading on BacTrack mobile app
 
Self Report of Intoxication Survey
 

80-90 minutes	
 
Participant receives third dose of alcohol containing vodka in fruit juice designed to raise the BrAC to 1.01-1.02 g/dL
 

90-110 minutes	
 
Participant rinses with alcohol free mouthwash or water
 

110-120 minutes	
 
Measurement of BrAC with BacTrack mobile breathalyzer
 
Control: Blinded to BrAC reading. Intervention: Shown BrAC reading on BacTrack mobile app
 
Self Report of Intoxication Survey
 

135 minutes	
 
Measurement of BrAC with BacTrack mobile breathalyzer
 
Control: Blinded to BrAC reading. Intervention: Shown BrAC reading on BacTrack mobile app
 
Self Report of Intoxication Rating Survey:
 

150 minutes	
 
Measurement of BrAC with BacTrack mobile breathalyzer
 
Control: Blinded to BrAC reading. Intervention: Shown BrAC reading on BacTrack mobile app
 
Self Report of Intoxication Rating Survey:
 

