### **Additional Information to Subjects**

**Whenever appropriate, the subjects will be provided with additional pertinent information after participation**

We will require a waiver of consent written consent in order to administer the screening survey over the phone because it is not feasible for each participant to be required to come in, in order to answer questions in the screening survey. Before the screening survey is administered, participants will be prompted to provide verbal consent (attached to this protocol) over the phone, using the verbal consent script that is attached to this protocol. Once a participant is screened, using the screener, and has set up a study session, participants will review and sign written informed consent at the beginning of their study visit prior to any other activities being completed.

**Potential Study Risks** **Describe and assess any potential risks associated with the research interventions (physical, psychological, social, economic, monetary, legal or other, loss of confidentiality) and assess the likelihood and seriousness of such risks. If methods of research create potential risks, describe other methods, if any, that were considered and why they will not be used.**

There is some risk that subjects will be identified as participants in the study and that the confidential information provided regarding psychiatric and substance use history will be inadvertently disclosed without the subjects' permission.

Urine pregnancy testing is performed for all women of reproductive potential, prior to alcohol administration, to avoid the potential for adverse fetal effects of alcohol. These procedures should add no additional risks beyond the minimal risks normally associated with them. Over a period of 120 minutes, participants will be given three doses of alcohol, which will result in a BrAC of 1.01-1.02g/dL. This amount of alcohol is equivalent to 4-5 standard drinks, an amount that these moderate-drinking subjects have ingested previously. Although the amount of alcohol available to them will produce only moderate blood alcohol levels, subjects could feel intoxicated or react negatively to the alcohol, such as nausea or dehydration. Engaging in any dangerous activities during this period would increase risk of self-harm. Precautions to minimize these risks are discussed below.

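### The final alcohol target is stated about ten-fold apart within the protocol (0.10 versus 1.01-1.02 g/dL), including in the dosing timeline, and must be reconciled

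*Combined protocol and SAP*

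**What the plan says.** The protocol states where the three doses are meant to bring the participant in six places.

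Three give 0.10:
- Brief description of the protocol: "The protocol involves consuming three weight-based doses of alcohol with a target BAC of 0.10" (no unit printed).
- Group Modifications: participants in each arm are to "consume three weight-based doses of alcohol with a target BAC of 0.10" (no unit printed).
- Administration of Surveys and/or Process: the doses are "designed to reach a peak blood alcohol level of .10 g/dL".

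Three give a figure just above 1:
- Study Design: the doses are "designed to raise Blood Alcohol Content to 1.02g/dL".
- Timeline, 80-90 minutes: "Participant receives third dose of alcohol containing vodka in fruit juice designed to raise the BrAC to 1.01-1.02 g/dL".
- Potential Study Risks: three doses over 120 minutes, "which will result in a BrAC of 1.01-1.02g/dL".

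The timeline also gives intermediate targets: a BrAC of 0.03-0.04 g/dL after the first dose and 0.07-0.08 after the second. Directly after its 1.01-1.02 figure, the risk section adds "This amount of alcohol is equivalent to 4-5 standard drinks" and says that "the amount of alcohol available to them will produce only moderate blood alcohol levels".

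**The concern.** All six statements describe the same three-dose regimen, yet they fall into two groups about ten-fold apart. The conflict sits in places that matter. The timeline row is the only third-dose target in the Procedures section, which staff are trained to follow. The survey administration and Study Design sections describe the weight- and gender-based doses as designed toward the stated target. The risk section uses the higher figure in the description on which the later Risk / Benefit Assessment relies.

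A reader therefore cannot tell from the document what exposure is intended, or to which exposure the reassurance about moderate levels applies.

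**Working it through.** **1. Like-for-like comparison.** Two statements use the same measure (blood) and the same unit (g/dL): .10 in the survey administration section and 1.02 in Study Design. So the conflict is not a matter of units, or of blood versus breath. Ratios across the stated figures:
- 1.01 / 0.10 = 10.1
- 1.02 / 0.10 = 10.2

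**2. Could blood versus breath explain the other pairs?** Study Instruments says the device estimates BAC to within 0.01 of a blood test. The gaps here are 1.01 − 0.10 = 0.91 and 1.02 − 0.10 = 0.92, roughly 90 times that tolerance.

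**3. Designed rise per dose.** Inputs are the timeline targets, starting from the confirmed zero reading. Each range runs from (lowest new target − highest previous target) to (highest new target − lowest previous target).

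| Dose | Calculation | Rise |
|---|---|---|
| 1 | from 0 | 0.03 to 0.04 |
| 2 | 0.07 − 0.04 to 0.08 − 0.03 | 0.03 to 0.05 |
| 3, if the end point is 0.10 | 0.10 − 0.08 to 0.10 − 0.07 | 0.02 to 0.03 |
| 3, if the end point is 1.01-1.02 | 1.01 − 0.08 to 1.02 − 0.07 | 0.93 to 0.95 |

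**4. Drink equivalence.** The same three doses are said to equal 4-5 standard drinks. Simple division, with no allowance for elimination, gives:
- 0.10 / 5 = 0.020 to 0.10 / 4 = 0.025 per drink
- 1.01 / 5 = 0.202 to 1.02 / 4 = 0.255 per drink

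One drink count cannot describe both targets. The risk section's reassurance that participants have drunk this amount before rests on that count, which mirrors the inclusion criterion of 4 drinks (women) or 5 (men).

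**5. Session length.** Participants stay until they reach about 0.03, in a session of 5-6 hours. Assume the peak is at minute 120 and the clock starts at the first dose, which leaves 3 to 4 hours. The average fall needed is (peak − 0.03) / hours:
- From 0.10: 0.07 / 4 = 0.0175 to 0.07 / 3 = 0.023 g/dL per hour
- From 1.01-1.02: 0.98 / 4 = 0.245 to 0.99 / 3 = 0.33 g/dL per hour

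Intake time before the first dose would make both steeper. The same schedule cannot have been planned around both figures.

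**6. Is it an isolated slip or a conversion artefact?** The higher figure appears in three separate sections, twice in running prose and once in a table row. Shifting the decimal point of 1.01-1.02 by one place gives 0.101-0.102. That range is 0.001 wide, against 0.01 for doses 1 and 2, and it is not the 0.10 printed elsewhere. The intended statement cannot be recovered mechanically and has to come from the authors.

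**The case against.** The strongest reply is that this is a contradiction on paper only. No dose amount is printed, dosing is tied to a published blood-alcohol prediction equation cited in Study Design and Dose Administration, and nobody can show from the document that a wrong dose would be prepared. That is true, and it limits the claim to what the text says. It does not settle the matter: the cited equation is not reproduced, and a prediction equation does not supply the intended target.

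A second reply points to the safeguards: stepped doses with a BrAC reading after each, a nurse on site, and monitored retention until levels fall. These are real, but they are means of detection and response. The 70-80 minute reading precedes the third dose, and nothing in the document makes that dose conditional on it. The later reading, the nurse and the retention rule all act after exposure.

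Two smaller objections stand. The switching between BAC and BrAC runs through the whole protocol and does not cause the ten-fold gap, so it is a secondary clean-up. The document also mentions no dose sheet or pharmacy order by name, saying only that the Investigational Drug Service supplies the alcohol. Any check must therefore be of whatever dosing record exists.

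**Conclusion.** The concern holds. The protocol states two final alcohol levels for one regimen, differing by a factor of 10.1 to 10.2, with no text to reconcile them. The higher figure stands in the operative timeline and in the risk section, so this is a must-fix item.

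The ratio and the third-dose steps use only printed figures and rest on one reading: that the 0.10 printed without a unit is in g/dL, as the survey administration section prints it. The hourly-fall comparison also needs the timing assumptions stated with it, and the conclusion does not depend on it. The finding is a contradiction in the document. It is not a claim that any participant would receive a ten-fold dose, and it takes no position on which figure is correct.

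**What to change.** The sponsor and investigator should reconcile the six places (the brief description, Group Modifications for both arms, Administration of Surveys and/or Process, Study Design, the 80-90 minute timeline row, and Potential Study Risks) so that one final target appears in all of them, in one unit. Naming one measure, BAC or BrAC, at the same time is a sensible tidy-up.

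Before any session, they should check whatever dose calculation or dispensing order exists against that single figure. They should also re-confirm the drink equivalence and the description of moderate levels in the risk section against it.

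The cost is a wording amendment in six places and one check of the dosing records. Sample size is unaffected. The primary model is also unaffected, because the Analysis Plan uses BrAC level and not the design target.

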### **Waiver Essential to Research\***

**The research could not be practicably carried out without the waiver or alteration**

It is not always feasible for participants to schedule a separate study visit to answer a brief screening survey. In order to accommodate participants who cannot schedule a separate study visit, we are requesting a waiver of written informed consent only to administer the screening survey over the phone. Allowing this step in the process to be completed over the phone will make the study more feasible to be completed by participants.

### **Additional Information to Subjects**

**Whenever appropriate, the subjects will be provided with additional pertinent information after participation**

We will require a waiver of consent written consent in order to administer the screening survey over the phone because it is not feasible for each participant to be required to come in, in order to answer questions in the screening survey. Before the screening survey is administered, participants will be prompted to provide verbal consent (attached to this protocol) over the phone, using the verbal consent script that is attached to this protocol. Once a participant is screened, using the screener, and has set up a study session, participants will review and sign written informed consent at the beginning of their study visit prior to any other activities being completed.

**Potential Study Risks** **Describe and assess any potential risks associated with the research interventions (physical, psychological, social, economic, monetary, legal or other, loss of confidentiality) and assess the likelihood and seriousness of such risks. If methods of research create potential risks, describe other methods, if any, that were considered and why they will not be used.**

There is some risk that subjects will be identified as participants in the study and that the confidential information provided regarding psychiatric and substance use history will be inadvertently disclosed without the subjects' permission.

Urine pregnancy testing is performed for all women of reproductive potential, prior to alcohol administration, to avoid the potential for adverse fetal effects of alcohol. These procedures should add no additional risks beyond the minimal risks normally associated with them. Over a period of 120 minutes, participants will be given three doses of alcohol, which will result in a BrAC of 1.01-1.02g/dL. This amount of alcohol is equivalent to 4-5 standard drinks, an amount that these moderate-drinking subjects have ingested previously. Although the amount of alcohol available to them will produce only moderate blood alcohol levels, subjects could feel intoxicated or react negatively to the alcohol, such as nausea or dehydration. Engaging in any dangerous activities during this period would increase risk of self-harm. Precautions to minimize these risks are discussed below.

After consuming alcohol, participants may be unsafe to operate a vehicle. This risk will be mitigated by providing participants transportation home with either a septa token or rideshare credits of up to \$30, depending on their location.

Study activities will be performed in a special clinical research room located in a hospital setting in close proximity to an inpatient care. Nursing and medical personnel will be available to assist in the care of the subject if any adverse event occurs. Participants' breath alcohol concentration (BrAC) and their general condition will be monitored during all aspects of the procedure. The bar-lab will be located in a safe and secure area in a hospital where medically trained staff will be onsite and there will be ready access to emergency care should it be necessary. All subjects will remain in the test area until their BrAC will be below 0.03 g/dL. All study activities will occur in the afternoon, no earlier than 11am, to minimize nausea and vomiting that could occur with morning alcohol consumption. A meal will be provided.

**Rating Scales and Questionnaires.** To avoid breach of confidentiality, subjects' names will appear only on a consent form, a telephone screening form and a "key" form kept in a locked cabinet. All forms that contain identifying information will be kept double locked (i.e., in a locked cabinet, in a locked room) to maintain their security. All study data forms will contain only the subject's unique study identification number, using a reference system maintained by the study staff. Completed study forms will be kept in a locked cabinet, the key to which will be available only to the PI and staff working on this study. Subject visits will be scheduled and no information about the subject will be provided to anyone (except in emergencies as defined above) in person or by telephone.

All paper research records will be stored in locked cabinets and only the investigators and only IRB approved study will have access to those records.

**Potential Study Benefits:** Assess the potential benefits to be gained by the individual subject, as well as benefits that may accrue to society in general as a result of the planned work (such as advancement of knowledge). Summary should also state if there are no direct benefits to subjects as a result of their participation in the study.

There are no benefits to participation. Participation may help us understand how smartphone-paired mobile breathalyzer devices impact behavior, which may lead to potential to help individuals better monitor their drinking behavior. In the future, this may help other people to manage their drinking habits and minimize risky drinking behavior.

